12. REGULATORY CONSIDERATIONS

12.1 Protocol Review and Amendments

This protocol, the proposed informed consent and all forms of participant information related to the study (e.g., advertisements used to recruit participants) and any other necessary documents must be submitted, reviewed and approved by a properly constituted IRB governing each study location.

Any changes made to the protocol must be submitted as amendments and must be approved by the IRB prior to implementation. Any changes in study conduct must be reported to the IRB. The Coordinating Center will disseminate protocol amendment information to all participating institutions.

All decisions of the IRB concerning the conduct of the study must be made in writing.

12.2 Informed Consent

All participants must be provided a consent form describing this study and providing sufficient information for participants to make an informed decision about their participation in this study. The formal consent of a participant, using an IRB approved consent form, must be obtained before the participant is involved in any study-related procedure. The consent form must be signed and dated by the participant or the participant's legally authorized representative, and by the person obtaining the consent. The participant must be given a copy of the signed and dated consent document. The original signed copy of the consent document must be retained in the research file.

12.3 Ethics and Good Clinical Practice (GCP)

This study is to be conducted according to the following considerations, which represent good and sound research practice:

- E6 Good Clinical Practice: Consolidated Guidance
www.fda.gov/downloads/RegulatoryInformation/Guidances/UCM129515.pdf
- US Code of Federal Regulations (CFR) governing clinical study conduct and ethical principles that have their origin in the Declaration of Helsinki o Title 21 Part 11 – Electronic Records; Electronic Signatures
www.access.gpo.gov/nara/cfr/waisidx_02/21cfr11_02.html
 - o Title 21 Part 50 – Protection of Human Subjects
www.access.gpo.gov/nara/cfr/waisidx_02/21cfr50_02.html
 - o Title 21 Part 54 – Financial Disclosure by Clinical Investigators
www.access.gpo.gov/nara/cfr/waisidx_02/21cfr54_02.html
 - o Title 21 Part 56 – Institutional Review Boards
www.access.gpo.gov/nara/cfr/waisidx_02/21cfr56_02.html It is understood that deviations from the protocol should be avoided, except when necessary to eliminate an immediate hazard to a research

participant. In such case, the deviation must be reported to the IRB according to the local reporting policy.

12.4 Study Documentation

The investigator must prepare and maintain adequate and accurate case histories designed to record all observations and other data pertinent to the study for each research participant. This information enables the study to be fully documented and the study data to be subsequently verified.

Original source documents supporting entries in the case report forms include but are not limited to hospital records, clinical charts, laboratory and pharmacy records, recorded data from automated instruments, microfiches, photographic negatives, microfilm or magnetic media, and/or x-rays.

12.5 Records Retention

All study-related documents must be retained for the maximum period required by applicable federal regulations and guidelines or institutional policies.

12.6 Multi-center Guidelines

12.6.1 Protocol Chair

The Protocol Chair is responsible for performing the following tasks:

- Coordinating, developing, submitting, and obtaining approval for the protocol as well as its subsequent amendments.
- Assuring that all participating institutions are using the correct version of the protocol.
- Taking responsibility for the overall conduct of the study at all participating institutions and for monitoring the progress of the study.
- Reviewing and ensuring reporting of Serious Adverse Events (SAE)
- Reviewing data from all sites.

12.6.2 Coordinating Center

The Coordinating Center is responsible for performing the following tasks:

- Ensuring that IRB approval has been obtained at each participating site prior to the first patient registration at that site, and maintaining copies of IRB approvals from each site.
- Managing central patient registration.
- Collecting and compiling data from each site.

- Establishing procedures for documentation, reporting, and submitting of AE's and SAE's to the Protocol Chair, and all applicable parties.
- Facilitating audits by securing selected source documents and research records from participating sites for audit, or by auditing at participating sites.

12.6.3 Participating Sites

Participating sites are responsible for performing the following tasks:

- Following the protocol as written, and the guidelines of Good Clinical Practice (GCP).
- Submitting data to the Coordinating Center.
- Registering all patients with the Coordinating Center by submitting patient registration form, and signed informed consent promptly.
- Providing sufficient experienced clinical and administrative staff and adequate facilities and equipment to conduct a collaborative trial according to the protocol.
- Maintaining regulatory binders on site and providing copies of all required documents to the Coordinating Center.
- Collecting and submitting data according to the schedule specified by the protocol.

13. STATISTICAL CONSIDERATIONS

13.1 Study Design/Endpoints

13.1.1 Definition of primary outcome/endpoint

The efficacy of SBRT delivered with a dose of 4000 cGy in 5 fractions on 800 cGy each to pediatric nonrhabdomyosarcoma soft tissue sarcoma or bone sarcoma patients who are greater than 3 years of age and \leq 40 years of age with metastatic disease will be determined by measuring local control at 6 months.

13.1.2 Analysis plan for primary endpoint

The primary endpoint of this study will be local control at 6 months of the patient treated with SBRT. Given the inherent difficulties in defining response in bony lesions after radiotherapy by RECIST 1.1 criteria, local control at the radiated site will be defined as the absence of progression of disease as defined in Section 9.1.4.1. Thus, CR and SD will constitute local control. Local control assessment will start at one month following completion of protocol treatment and continuous assessment will be pursued during the follow-up period. The reference response probability for comparison will be 70%. This is based on the study by Kepka et al. (31)

13.2 Sample Size/Accrual Rate

The primary endpoint of this trial is to estimate the local control of SBRT at 6 months. We anticipate that the local control rate will be roughly 90% as opposed to a 70% historical response with conventional moderate dose radiation. With 20 subjects participated, we will be able to estimate the local control rate to within 20% (i.e., maximum width of the 90% confidence interval reached is when the observed rate is 50%). If we observe a 6-month local control rate of 90%, we will be 90% certain that the true rate is greater than 70%. The associated exact 90% confidence interval will be (0.72, 0.98).

Using a Simon optimal two-stage design with a type I error of 10% and a type II error of 20%, the first stage would consist of 6 patients. A responder is considered to have local disease control at 6 months. If 4 or fewer patients respond, the study would terminate after the first stage. Otherwise, accrual would continue to a total of 20 patients. If 17 or more patients respond at the end of the second stage, the regimen with SBRT is considered promising (i.e., local control at 6 months is greater than 70%). This design has a 58% chance of early stopping when the true probability of response is 70% (the null hypothesis) and 11% chance of early stopping when the true probability of response is 90%.

The goal of enrollment is 20 patients. Based on the current institutional referral base, we expect that 12 patients will be eligible each year. Of these patients, we expect that two thirds will enroll on protocol. With this projection, we plan to complete accrual to the study in 3 years.

The proportion of patients with local control at six months will be reported with an exact binomial 90% confidence interval.

13.3 Analysis of Secondary Endpoints

13.3.1 Definition of secondary outcomes/endpoints:

- To describe the toxicity of SBRT delivered to a dose of 4000 cGy in 5 fractions of 800 cGy each for the population enrolled using grading with CTCAE v. 4.0
- The clinical response rate of each lesion will be assessed by serial CT assessment (FDG-PET/CT is optional for assessment) and defined by criteria as defined above. The absence of progression will constitute a response. Therefore, lesionspecific CR or SD will be measured as a response.
- To assess long-term clinical outcomes of this patient population after completion of SBRT by measuring relapse-free survival and overall survival. Relapse-free survival will be measured from time of enrollment to date of disease progression or death. Patients who are lost to follow-up will be censored for determination of

progression-free survival on the date of their last evaluation. Overall survival is defined as time from enrollment to death due to any cause.

- To assess quality of life following completion of SBRT using pre- and post-SBRT completion of the Brief Pain Inventory form and 10 point Visual Analog Scale which will be filled out by the patient at the treatment response intervals outlined above.

13.3.2 Analysis plan for secondary endpoints:

- Toxicities will be graded and tabulated at the time of each follow-up assessment. The proportion of toxicities by type and grade will be reported with exact 95% confidence intervals.
- Each metastatic lesion will be considered a target lesion and independently evaluated for response. The proportion of these lesions that have a stable or better response and the intra-cluster correlation will be estimated with an intercept only generalized estimating equation (GEE) regression. This will be estimated directly with SAS Genmod by specifying binomial variation, the identity link function, and an exchangeable correlation structure.
- Hazard rate estimates and 95% confidence intervals as well as Kaplan-Meier (KM) estimates will be used to summarize survival (OS), progression free survival (PFS), time to progression (TTP) and locoregional control (LRC) functions over time. The median OS, PFS, TTP and LRC will be reported. Cox proportional hazards models will be used to evaluate the impact of key covariates on these endpoints as the sample size permits.
- Quality of life will be assessed using the Brief Pain Inventory form and 10 point Visual Analog Scale. An overall score will be calculated pre-treatment and at the time of the 2nd radiologic reassessment. The change in score will be evaluated with a Wilcoxon signed-rank test.

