1. OBJECTIVES

1.1 Primary Objectives

To determine the lesion-specific local control at 6 months of SBRT delivered to a dose of 4000 cGy in 5 fractions of 800 cGy each for patients greater than 3 years of age and ≤ 40 years of age with metastatic disease of bone secondary to pediatric non-rhabdomyosarcoma soft tissue or bone sarcoma.

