3. PATIENT SELECTION

3.1 Inclusion Criteria

- 3.1.1 Patients must have histologically or cytologically confirmed nonrhabdomyosarcoma of soft tissue or bone at any site
- 3.1.2 Patients must have measurable disease, defined as at least one lesion that can be accurately measured in at least one dimension (longest diameter to be recorded) as ≥ 20 mm with conventional techniques or as ≥ 10 mm with spiral CT scan within 4 weeks of treatment start. See Section 9.1.3 for the evaluation of measurable disease.
- 3.1.3 Greatest tumor dimension of all sites must be ≤ 5.0 cm or <250 cm^3
- 3.1.4 There is at least 1 metastatic site at one or more of the following sites: spine or non-spine bone and at maximum 5 sites can be treated on protocol
- 3.1.5 Surgically unresectable site as determined by tumor board or surgeon or patients who decline surgery.
- 3.1.6 Patients must be greater than 3 years of age and ≤ 40 years of age.
- 3.1.7 Life expectancy of at least 9 months
- 3.1.8 Lansky performance status ≥ 50 (See Appendix E)
- 3.1.9 Ability to understand and the willingness to sign a written informed consent document and if a minor, have a guardian who meets the above criteria.

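### Section 13.3.2 names no confidence interval for the lesion-level control rate, and the symmetric interval its identity-link GEE yields by default would under-cover with at most 20 patients and control near 90%

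*Combined protocol and SAP*

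**What the plan says.** Section 13.3.2 treats each metastatic lesion as a target lesion. It estimates the proportion with stable or better response, and the ICC, by an intercept-only GEE in SAS Genmod, "specifying binomial variation, the identity link function, and an exchangeable correlation structure". The outcome is binary for each lesion: "The absence of progression will constitute a response" (Section 13.3.1). No time point is given there.

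The setting comes from other sections:

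- Clusters: "The goal of enrollment is 20 patients" (Section 13.2). If the trial stops early there are fewer, since "the first stage would consist of 6 patients".
- Lesions per patient: at least one, and "at maximum 5 sites can be treated on protocol" (Section 3.1). No distribution is given.
- Rate: "We anticipate that the local control rate will be roughly 90% as opposed to a 70% historical response" (Section 13.2).

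For the lesion-level proportion the plan states no interval, confidence level, small-sample correction or rule for the case where every lesion is controlled. It does name intervals elsewhere: exact binomial 90% for the primary patient-level rate (Section 13.2), and exact 95% for toxicity and 95% for hazard rates (Section 13.3.2).

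**The concern.** A proportion near 0.90 from 20 or fewer clusters is a poor setting for a symmetric large-sample interval. On the identity scale, estimate plus or minus a multiple of the standard error can run past 1. The standard error shrinks as the estimate approaches 1, and it is zero when no lesion fails. The robust variance is also known only approximately with so few clusters. If the analyst takes the interval that goes with the stated model, the precision of the lesion-level rate will be overstated.

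This could matter in reporting because Section 1.1 words the primary objective at lesion level: "To determine the lesion-specific local control at 6 months of SBRT". The primary analysis counts patients, so readers may look to the GEE result for the lesion-specific answer.

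**Working it through.** **Inputs.** From the documents: 20 patients (6 if stopped at stage 1), 1 to 5 lesions each, anticipated control 90%. The 90% is stated for 6-month local control and is borrowed here for the lesion rate. Assumed, because the documents are silent: lesions per patient (all 1; mostly 1-2; uniform 1-5; all 5), ICC 0 to 0.5, and a robust-SE Wald interval as the default.

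**Step 1: the plan's own figures.** The exact 90% interval for 18/20 is 0.717 to 0.982 (stated 0.72, 0.98). Early stopping is 58.0% at a true rate of 70% and 11.4% at 90% (stated 58% and 11%). These reproduce.

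**Step 2: formulas.** For patient i with m_i lesions, s_i controlled, and w_i = 1/(1 + (m_i - 1) × ICC):

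- estimate p = Σ w_i s_i / Σ w_i m_i
- robust SE = √Σ[w_i (s_i - m_i p)]² / Σ w_i m_i
- default interval: p ± z × SE
- logit interval: ln(p/(1-p)) ± z × SE/(p(1-p)), back-transformed

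The link does not enter p or the ICC. One test dataset fitted with both links gave 0.863 and 0.229 each time.

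**Step 3: one lesion per patient, by hand.** Here SE = √(p(1-p)/20).

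- 18/20: SE = √(0.9 × 0.1/20) = 0.0671. The 90% Wald interval is 0.9 ± 1.645 × 0.0671 = 0.790 to 1.010, against the plan's exact 0.72 to 0.98.
- 17/20: SE = 0.0798. The 90% Wald lower limit is 0.85 - 1.645 × 0.0798 = 0.719, above the 70% reference. The exact lower limit is 0.656, below it.
- At 95%, the Wald upper limits for 16, 17, 18 and 19 of 20 are 0.975, 1.006, 1.031 and 1.046. At a true 90%, the chance of 17, 18 or 19 is 0.190 + 0.285 + 0.270 = 74.5%.
- All 20 controlled (SE zero): 0.9^20 = 12.2%.
- The 95% Wald interval contains 0.90 for 14 to 19 controlled, so coverage is 1 - 0.122 - 0.002 = 87.6%. In this case almost all the shortfall comes from trials with no failure.
- The 95% logit interval for 18/20: 2.197 ± 1.96 × 0.745 gives 0.736 to 3.658, or 0.676 to 0.975 as a proportion. With the Mancl-DeRouen factor 20/19 and t(19) = 2.093, it is 0.635 to 0.979.

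**Step 4: several lesions per patient, by simulation.** Lesions were beta-binomial within patient, with 6,000 trials per scenario (3,000 with 6 clusters). Simulation error at 87% coverage is √(0.87 × 0.13/6000) = 0.4 points. For 20 clusters, true rate 90% and nominal 95% Wald:

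| Lesions per patient | Upper limit above 100% (ICC 0 to 0.5) |
|---|---|
| all 1 (exact) | 74.5% |
| mostly 1-2 | 41-66% |
| uniform 1-5 | 16-58% |
| all 5 | 1.5-46% (about 2-6% at ICC 0 to 0.1) |

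Coverage over all these scenarios is about 81-93%, counting trials with no failure as misses. At a true rate of 80% it is 87-92%. With 6 clusters and a 90% rate it is 47-77%.

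**Step 5: which part is at fault.** Among trials with at least one failure (20 clusters, 90% rate):

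| Interval | Coverage | Above 100% |
|---|---|---|
| identity, Mancl-DeRouen, t(19), more than one lesion each | 87-95% | 3-84% |
| logit, ordinary robust SE | 91-97% | never |
| logit, Mancl-DeRouen, t(19) | 93-99% | never |

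Like for like, with a mean of 1.75 or 2.35 lesions, ICC 0.1 to 0.5 and trials with no failure left out, the default interval covers 85-89% and the corrected logit interval 96-98%. Changing only the scale recovers most of the loss; correcting only the SE does not.

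**The case against.** The strongest reply is that the criticised interval is not in the plan. Section 13.3.2 says the proportion will be estimated, and the authors name an interval where they want one. A GEE does not fix the type of SE, the scale, the reference distribution or the level. This stands: the documented fault is an omission, and the under-coverage belongs to the default that would fill it. It does not remove the point, because an estimate from 20 clusters needs an interval and the one closest to hand is poor.

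Five stronger readings are tempting, and the documents do not support them.

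- *The identity link distorts the estimate.* It does not; in an intercept-only model the proportion and ICC are the same under either link.
- *The sandwich SE is the main culprit.* It is not. With a mean of 2.35 lesions and ICC 0.3, robust and model-based SEs on the identity scale give coverage within 0.3 points of each other (86.2% and 86.5%). The symmetric scale near 1 is the main cause, and the few clusters add to it.
- *The limit will usually exceed 100%.* That depends on lesion counts and ICC, which the documents do not give; the range is about 1.5% to 75%.
- *This is the only lesion-level analysis.* That is not established. Section 9.1.6 defines local control by the target lesion, and Section 13.3.2 plans Kaplan-Meier summaries of locoregional control whose unit is unclear.
- *The trial's conclusion is at risk.* It is not. The decision rule counts patients and the primary rate has an exact interval. The mismatch between the lesion-specific wording of Section 1.1 and the patient-level analysis is a separate question.

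**Conclusion.** The concern holds in a limited form. The plan leaves the interval for the lesion-level rate unspecified, and the default from its stated model would be too optimistic: about 81-93% coverage at nominal 95% with 20 patients and 90% control. Under-coverage appears in every lesion pattern and ICC examined, though with one lesion per patient it comes almost wholly from trials with no failure. Impossible upper limits are common (about 40-75%) only when most patients have one or two lesions. They are rare (about 2-6%) with five lesions each and an ICC of 0.1 or less.

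These figures rest on assumed lesion counts, an assumed ICC range, beta-binomial clustering, the 90% rate borrowed from Section 13.2, and a robust Wald interval as the default. The consequence is confined to the reported precision of a secondary estimate. That estimate may still carry weight in reporting because of how Section 1.1 is worded.

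**What to change.** Keep the GEE as specified and add to Section 13.3.2:

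- The 95% interval for the lesion-level proportion is built on the logit scale and back-transformed.
- Preferably, it uses a small-sample-corrected sandwich variance (for example Mancl-DeRouen) and a t reference with patients minus 1 degrees of freedom.
- If every lesion is controlled, neither link gives a usable interval (0-12% of trials at a 90% rate), so an exact patient-level interval is reported. For 20 of 20 patients the exact 95% lower limit is 0.025^(1/20) = 0.832.

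The cost is a short text change and a small amount of programming. The point estimate and ICC do not move. The interval becomes somewhat wider and can be slightly conservative (up to 99% coverage in the scenarios above). It is not a complete cure, since coverage was as low as 93% in the least favourable scenario.

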5.6.2 At 3, 6, 9, 12, 18, 24, 30, and 36 months Post-SBRT

5.7 Duration of Follow-Up

It is anticipated the patients that remain on-study will be followed for 3 years.

Patients will remain enrolled on this protocol until there is evidence that their disease has progressed either locally or distally, at which case they will be removed from the protocol and be followed for survival only. Patients removed from study for unacceptable adverse events will be followed per protocol until resolution or stabilization of the adverse event and then followed for survival only.

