8. STUDY CALENDAR

Note that the study calendar is based on the ideal subject. The schedule should be followed as closely as realistically possible, but may be modified due to problems such as scheduling delays, conflicts such as clinic closure or poor weather conditions, or other unforeseeable events.

	Pre-Study ¹	SBRT ^{3,9}	Follow-up (in time Post-RT)									
			4 weeks (± 7 days)	3 mo ⁶	6 mo ⁶	9 mo ⁶	12 mo ⁶	18 mo ⁷	24 mo ⁷	30 mo ⁷	36 mo ⁷	
Informed Consent	X											
Demographics	X											Follow for survival
Medical History	X											
Physical Exam	X		X	X	X	X	X	X	X	X	X	
Height	X											
Weight & Vitals	X	X	X	X	X	X	X	X	X	X	X	
Performance Status	X	X	X	X	X	X	X	X	X	X	X	
Biopsy-confirmed sarcoma	X											
Treatment planning scan	X											
CBC w/ diff, plts, CMP	X ₄		X	X	X	X	X	X	X	X	X	
CT of treatment site	X ₈			X	X	X	X	X	X	X	X	
MRI	X ₅			X ₁₁	X ₁₁	X ₁₁	X ₁₁	X ₁₁	X ₁₁	X ₁₁	X ₁₁	
FDG-PET (optional)	X			X ₁₁	X ₁₁	X ₁₁	X ₁₁	X ₁₁	X ₁₁	X ₁₁	X ₁₁	
Tumor measurements	X			X	X	X	X	X	X	X	X	
Pregnancy test ²	X											
Pain Assessments ¹⁰	X	X	X	X	X	X	X	X	X	X	X	
Toxicity Assessment		X	X	X	X	X	X	X	X	X	X	

¹Pre-SBRT assessments should be performed within 4 weeks of radiation treatment

²Pregnancy test by urine or serum, for women who are not post-menopausal as defined in Appendix A

³ Patients will receive SBRT over a five-day period. Ideally all 5 fractions should be delivered Monday through Friday, however it may be delivered over two weeks
⁴ Within 1 week prior to radiotherapy
⁵ Optional depending on treatment site
⁶ Follow-up should occur +/- 14 days
⁷ Follow-up should occur +/- 30 days
⁸ CT scan must be performed within 4 weeks prior to the start of therapy, not required if MRI is obtained.
⁹ Patients will be able to receive chemotherapy 2 weeks after the completion of SBRT.
¹⁰ Brief Pain Inventory (Appendix C) and 10 point Visual Analog Scale (Appendix F); given the age population, the completion of these assessments may not be possible and therefore are optional for subjects under 18 years of age
¹¹ Follow-up PET/CT and MRI are at the discretion of the treating physician and are optional

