9. MEASUREMENT OF EFFECT

9.1 Antitumor Effect – Solid Tumors

For the purposes of this study, patients should be re-evaluated for response 4 weeks after the initial treatment, every 3 months for the first year, and every 6 months for the second and third year.

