APPENDIX C Brief Pain Inventory Form

STUDY ID# _____

HOSPITAL # _____

DO NOT WRITE ABOVE THIS LINE

Brief Pain Inventory (Short Form)

Date: ____ / ____ / ____

Time: ____

Name: _____

Last

First

[figure not shown]
Middle Initial

1. Throughout our lives, most of us have had pain from time to time (such as minor headaches, sprains, and toothaches). Have you had pain other than these everyday kinds of pain today?

1. Yes

2. No

2. On the diagram, shade in the areas where you feel pain. Put an X on the area that hurts the most.

3. Please rate your pain by circling the one number that best describes your pain at its **worst** in the last 24 hours.

4. Please rate your pain by circling the one number that best describes your pain at its **least** in the last 24 hours.

5. Please rate your pain by circling the one number that best describes your pain on the **average**.

6. Please rate your pain by circling the one number that tells how much pain you have **right now**.

7. What treatments or medications are you receiving for your pain?

8. In the last 24 hours, how much relief have pain treatments or medications provided? Please circle the one percentage that most shows how much relief you have received.

0% 10% 20% 30% 40% 50% 60% 70% 80% 90% 100%
No Complete
Relief Relief

9. Circle the one number that describes how, during the past 24 hours, pain has interfered with your:

A. General Activity

0 1 2 3 4 5 6 7 8 9 10
Does not Completely
Interfere Interferes

B. Mood

0 1 2 3 4 5 6 7 8 9 10
Does not Completely
Interfere Interferes

C. Walking Ability

0 1 2 3 4 5 6 7 8 9 10
Does not Completely
Interfere Interferes

D. Normal Work (includes both work outside the home and housework)

0 1 2 3 4 5 6 7 8 9 10
Does not Completely
Interfere Interferes

E. Relations with other people

0 1 2 3 4 5 6 7 8 9 10
Does not Completely
Interfere Interferes

F. Sleep

0 1 2 3 4 5 6 7 8 9 10
Does not Completely
Interfere Interferes

G. Enjoyment of life

0 1 2 3 4 5 6 7 8 9 10
Does not Completely
Interfere Interferes

Copyright 1991 [name]
Pain Research Group
All rights reserved.

Used by permission.

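### The quality-of-life test uses one undefined score at one visit and drops patients who progress or die before it, leaving their earlier pain forms unused

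*Combined protocol and SAP*

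**What the plan says.** Quality of life is a secondary objective (Section 1.2.4). Its analysis, in Section 13.3.2, is three sentences. They name two instruments ("Quality of life will be assessed using the Brief Pain Inventory form and 10 point Visual Analog Scale"), one score at two times ("An overall score will be calculated pre-treatment and at the time of the 2nd radiologic reassessment") and one test ("The change in score will be evaluated with a Wilcoxon signed-rank test"). No significance level, effect size or rule for missing forms is given.

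Collection is much wider than analysis. Section 13.3.1 has the forms completed repeatedly: "which will be filled out by the patient at the treatment response intervals outlined above". The calendar in Section 8 schedules pain assessments pre-study, during SBRT, at 4 weeks, and at 3, 6, 9, 12, 18, 24, 30 and 36 months.

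Two provisions limit who supplies a form. Section 5.7: "Patients will remain enrolled on this protocol until there is evidence that their disease has progressed either locally or distally"; after that, follow-up is for survival only. Footnote 10 of the calendar says of the pain forms that "the completion of these assessments may not be possible and therefore are optional for subjects under 18 years of age".

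On timing, the calendar's CT and tumor-measurement rows are empty at 4 weeks and begin at 3 months. Section 9.1, however, says that "patients should be re-evaluated for response 4 weeks after the initial treatment", and Section 13.1.2 starts local control assessment at one month.

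**The concern.** A paired test at one late visit can use only patients who have a form there. Because progression ends form collection, whether a patient is in the test depends on outcome. Take a patient whose progression is found at 3 months. That patient will have been due forms at baseline, 4 weeks and 3 months, yet contributes nothing to a 6-month comparison. If such patients have worse pain than those who remain, the average change in the test is more favourable than the average change in everyone treated. In a single-arm trial there is no control group in which the same selection would show.

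The undefined score adds a second problem: two analysts could build different scores from the same forms. At stake is whether a reported improvement in pain after SBRT describes the treated patients or only those still on protocol, and whether the score can be reproduced. No efficacy or stopping decision depends on it.

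**Working it through.** The plan gives no power or sample-size figure for this analysis, so there is nothing to reproduce. The checks are as follows.

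**1. Data used.** The calendar gives 3 occasions up to 4 weeks (pre-study, SBRT, 4 weeks) plus 8 later visits, so 3 + 8 = 11. The test uses 2; the other 9 have no planned analysis.

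**2. Which visit.** By the CT row, the first follow-up imaging is at 3 months and the second at 6 months. If the 4-week evaluation in Section 9.1 counts as the first reassessment, the second is at about 3 months. The plan refers to a radiologic reassessment and the calendar shows no imaging at 4 weeks, so 6 months is the better reading. The procedure lists under Sections 5.6.1 and 5.6.2 are not in the available text and cannot settle it.

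**3. Number of pairs.** Planned N is 20 (Section 13.2). The proportion still on protocol at the visit and the proportion completing forms are not in the documents; the values below are assumptions. Pairs = 20 × proportion on protocol × completion.

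| On protocol | 100% complete | 70% complete | 50% complete |
|---|---|---|---|
| 80% | 16 | 11.2 | 8 |
| 60% | 12 | 8.4 | 6 |
| 40% | 8 | 5.6 | 4 |

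If the trial ends after the first stage of 6 patients (Section 13.2), there can be at most 6 pairs.

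**4. What the test can show.** The smallest two-sided exact signed-rank p-value with n pairs is 2/2^n:
- n = 4: 2/16 = 0.125
- n = 5: 2/32 = 0.0625
- n = 6: 2/64 = 0.031, reached only if every patient changes in the same direction

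Simulated power at a two-sided 5% level (assumed, since none is stated) for a mean change of 0.8 SD is about 91% with 20 pairs, 82% with 16, 68% with 12, 44% with 8, 22% with 6 and zero with 5.

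**5. Selection.** Assume the true mean change over all 20 patients is zero, that patients who progressed before the visit score 1 SD worse than the others, and that everyone still on protocol completes the form. With proportion *p* still on protocol, their mean change is −(1 − *p*) SD, where negative means less pain: −0.2, −0.4 and −0.6 SD at *p* = 80%, 60% and 40%. In simulation the test then wrongly shows improvement in about 11%, 23% and 26% of trials, against a nominal 2.5% in that direction. The 1 SD gap is an illustration, not a figure from the documents.

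**6. Score definition.** Appendix C has four severity ratings (items 3–6, taken as higher is worse; their number scales are not visible in the text), seven interference items (9A–9G, 0–10, higher is worse) and item 8, "In the last 24 hours, how much relief have pain treatments or medications provided", answered from 0 to 100% (higher is better). Suppose all 11 severity and interference items improve by 2 points and relief rises by 30 percentage points. The total then depends on how item 8 is handled:
- item 8 left out: 11 × (−2) = −22
- item 8 divided by 10 but not reversed: −22 + 3 = −19
- item 8 added as recorded: −22 + 30 = +8, an apparent worsening

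The plan does not say which of these, if any, is meant, or whether the visual analog scale is part of the score.

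**The case against.** The strongest defence is that one pre-specified comparison limits multiplicity in a trial of 20, that nothing bars descriptive summaries of other visits, and that a secondary single-arm endpoint carries no decision. The last part stands and limits the weight of the point. The first does not answer the selection problem: fewer comparisons do not make the retained patients representative. Section 13.4.2 asks that conclusions rest on all enrolled subjects, but it sits under evaluation of response and gives no method for missing pain forms.

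A second objection is that a mixed model is fragile in small numbers and cannot recover pain after progression. That is right, and it is why the model should be kept simple and its assumption stated. It does use the earlier forms of patients who later progress, which the signed-rank test discards.

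A reader might also infer stronger things that the documents do not support:
- **That the score does mix items running in opposite directions.** No section lists its items, so item 8 may be left out. This is a risk.
- **That 3 and 6 months are equally supported.** The calendar favours 6.
- **That only the best responders remain, or that every progressor is lost.** Patients with stable disease stay on protocol, and a patient whose progression is first found at the 6-month visit can still complete a form there.
- **That the test cannot reach significance.** This holds only with 5 or fewer pairs and a 5% level. Forms are optional, not excluded, under 18, so the number of adults does not cap the number of pairs.

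**Conclusion.** The point holds as a should-fix on a secondary endpoint. The documents establish three things: the score is undefined; only one of the scheduled post-treatment assessments is tested; and patients who progress or die before that visit have no planned form there. Optional completion under 18 can narrow the group further.

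That the result will look too favourable is likely but not certain. It requires that patients who leave have worse pain changes than those who stay, and its size (false improvement in about 11% to 26% of trials in the illustration) rests on the assumed 1 SD gap and on 40% to 80% remaining on protocol. The number of pairs cannot be determined; the assumed ranges give 4 to 16. The p-value floor of 0.0625 at 5 pairs is exact. The primary endpoint and its decision rule are untouched.

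**What to change.** Revise the quality-of-life paragraph in Section 13.3.2:

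- Define three separate scores: pain severity (mean of items 3–6), pain interference (mean of items 9A–9G) and the visual analog scale. Leave item 8 out of the scores.
- Fit a simple repeated-measures mixed model to each score, with visit as a factor and a random intercept for patient, on the baseline, 4-week, 3-month and 6-month forms. Report the estimated change from baseline at each visit with a confidence interval, as descriptive results.
- At each visit, report the number of forms and the reasons for missing ones (progression, death, under 18 and not completed, other).
- Replace the count of reassessments by a named month, 6 months on the calendar reading, and keep the signed-rank test there as supportive.
- State that the model assumes forms are missing at random given the observed scores.

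The cost is a change of wording and slightly more analysis, with no new data. Three scores at several visits mean more estimates, which is acceptable if none is presented as confirmatory. Selection after progression is reduced, not removed: pain after progression remains unobserved, and the report should say so.
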